6.1.8 DOSE ADJUSTMENTS/MODIFICATIONS/DELAYS

GENERAL MANAGEMENT OF DOSE ADJUSTMENT S/MODIFICATIONS WITH IBRUTINIB AND/OR PEMBROLIZUMAB

Below is the table for general management/adjustments of ibrutinib and pembrolizumab for hematologic and non-hematologic adverse events.

If study treatment is held for an adverse event and the subject is approved to resume treatment, the subject will resume with the timepoint at which the treatment was held.

Toxicity	Grade	Dose Modification	Toxicity Management	Agent to be considered for dose modification
Thrombocytopenia (Unless it is related to CLL bone marrow involvement)	1,2 3 (Platelets < 50 000 cells/mm ³ [50×10^9])	N/A Ibrutinib: No dose modification required Pembrolizumab: No dose modification required	N/A Monitor CBC/differential at least weekly Platelet transfusions are permitted per AABB guidelines	Ibrutinib Pembrolizumab

Ibrutinib and PD-1 Blockade to Improve Immune Dysfunction in
Chronic Lymphocytic Leukemia
Protocol <#>

	4 (Platelets < 25 000 cells/mm ³ [50×10^9])	
Ibrutinib: If thrombocytopenia resolves to \leq Grade 1 (platelets $\geq 75,000$ cells /mm³ [75×10^9/L] or baseline, restart the dose. If toxicity recurs, reduce dose by 140 mg. If toxicity persists following two dose reductions, discontinue ibrutinib
 
Pembrolizumab: Decision to discontinue will depend upon clinical situation and per clinical investigator's judgment and in consultation with Supporting company
	Monitor CBC/differential at least weekly Platelet transfusions are permitted per AABB guidelines	
Neutropenia (Unless it is related to CLL bone marrow involvement)	1,2	N/A	N/A	Ibrutinib Pembrolizumab
	3 ANC < 1000 cells/m ³ [1×10^9])	
Ibrutinib Hold ibrutinib if Grade 3 associated with infection or fever (temperature $\geq 38.5^{\circ}\text{C}$) If neutropenia resolves to \leq Grade 1 (ANC ≥ 1500 /mm³ [$\geq 1.5 \times 10^9$ /L]) or baseline, restart the dose. If toxicity recurs, reduce dose by 140 mg. If toxicity persists following 2 dose reductions, discontinue the drug
 
Pembrolizumab Hold pembrolizumab until resolution to \leq Grade 1 or baseline For AEs that downgrade to \leq Grade 2 within 7 days or resolve to \leq Grade 1 or baseline within 14 days, resume IP/study regimen administration at next scheduled dose. Otherwise, discontinue pembrolizumab
	Monitor CBC/differential at least weekly Use of myeloid growth factors (MGF) are permitted per ASCO or NCCN guidelines	

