	4 ANC < 500 cells/m ³ [1×10^9])	
Ibrutinib Hold ibrutinib for Grade 4 If neutropenia resolves to \leq Grade 1 (ANC ≥ 1500 /mm³ [$\geq 1.5 \times 10^9$ /L]) or baseline, restart the dose. If toxicity recurs, reduce dose by 140 mg. If toxicity persists following 2 dose reductions, discontinue the drug
 
Pembrolizumab Decision to discontinue will depend upon clinical situation and per clinical investigator's judgment and in consultation with supporting company
	Monitor CBC/differential at least weekly Use of myeloid growth factors (MGF) are permitted per ASCO or NCCN guidelines	
Non-Hematological	1	N/A		Pembrolizumab

toxicity (non-immune related toxicity)	2	Pembrolizumab Hold drug until resolution to Grade \leq 1 toxicity or baseline Ibrutinib No dose interruption is needed		Ibrutinib
	3 or 4	Pembrolizumab Hold drug until resolution to Grade \leq 1 toxicity or baseline For AEs that downgrade to \leq Grade 2 within 7 days or resolve to \leq Grade 1 or baseline within 14 days, resume IP/study regimen administration at next scheduled dose. Otherwise, discontinue pembrolizumab For Grade 4 AEs the decision to discontinue will depend upon clinical situation and per clinical investigator's judgment and in consultation with supporting company Ibrutinib Hold Ibrutinib If toxicity resolves to \leq Grade 1 or baseline, restart the dose. If toxicity recurs, reduce dose by 140 mg. If toxicity persists following two dose reductions, discontinue ibrutinib		

IBRUTINIB DOSE MODIFICATIONS

Interrupt ibrutinib therapy for any Grade 3 or greater non-hematological toxicities, Grade 3 or greater neutropenia with infection or fever, or Grade 4 hematological toxicities. Once the symptoms of the toxicity have resolved to Grade 1 or baseline (recovery), ibrutinib therapy may be reinitiated at the starting dose. If the toxicity reoccurs, reduce dose by one capsule (140 mg per day). A second reduction of dose by 140 mg may be considered as needed. If these toxicities persist or recur following two dose reductions, discontinue ibrutinib.

Recommended dose modifications are described below:

Toxicity occurrence	Withhold/Discontinue ibrutinib?
First	Restart at 420 mg daily
Second	Restart at 280 mg daily
Third	Restart at 140 mg daily
Forth	Discontinue ibrutinib

MANAGEMENT/SUPPORTIVE CARE OF IMMUNE RELATED ADVERSE EVENTS RELATED TO PEMBROLIZUMAB

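### Section 6.1.8 sets two recovery grades for restarting pembrolizumab after Grade 3 non-immune non-hematological toxicity or Grade 3 neutropenia, so an event that settles at Grade 2 within 7 days is both held and re-dosed

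*Combined protocol and SAP*

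**What the plan says.** All the text is in the dose-modification table of section 6.1.8.

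- **Non-hematological, Grade 3 or 4 row.** The pembrolizumab entry opens "Hold drug until resolution to Grade \leq 1 toxicity or baseline For AEs that downgrade to \leq Grade 2 within 7 days" and continues "or resolve to \leq Grade 1 or baseline within 14 days, resume IP/study regimen administration at next scheduled dose". It then says "Otherwise, discontinue pembrolizumab For Grade 4 AEs the decision to discontinue will depend upon clinical situation".
- **Non-hematological, Grade 2 row.** "Hold drug until resolution to Grade \leq 1 toxicity or baseline Ibrutinib No dose interruption is needed".
- **Neutropenia, Grade 3 row.** "Hold pembrolizumab until resolution to \leq Grade 1 or baseline For AEs that downgrade to \leq Grade 2 within 7 days", followed by the same 14-day alternative and ending "resume IP/study regimen administration at next scheduled dose. Otherwise, discontinue pembrolizumab".
- **Neutropenia, Grade 1 and 2 row.** Marked not applicable; it gives no pembrolizumab instruction.

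The non-hematological rows are limited by their label, "toxicity (non-immune related toxicity". Immune-related events and infusion reactions have their own tables later in the same section.

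**The concern.** Each Grade 3 entry has three parts: a hold sentence, a resume sentence and a stop sentence. The hold sentence ends at Grade 1 or baseline. The resume sentence is also satisfied at Grade 2, provided that grade is reached within 7 days. A patient can meet the second condition without meeting the first, and the table does not say which sentence prevails. The non-hematological Grade 2 row adds a third text bearing on the same patient, and it agrees with the hold sentence against re-dosing.

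The rule decides whether a patient with unresolved toxicity is given pembrolizumab again and, on slower recovery paths, whether the drug is stopped for good. The trial is single-arm with 25 patients, and safety of the combination is a secondary endpoint (section 4.2.2). Exposure to the combination, and the count of patients taken off pembrolizumab for toxicity, could therefore depend in part on which sentence an investigator follows.

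**Working it through.** The plan gives no figure to reproduce here; the check sets the rules side by side and applies each one to the same recovery paths.

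**Rules, from section 6.1.8**
- Hold sentence: hold while above Grade 1 (or baseline); no time limit.
- Resume sentence: resume at the next scheduled dose if Grade 2 or lower within 7 days, or Grade 1 or baseline within 14 days.
- Stop sentence: otherwise discontinue.
- Grade 2 row (non-hematological only): hold until Grade 1 or baseline.

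**Assumptions.** Baseline is Grade 0. Improvement does not reverse. The 7 and 14 days run from onset, since the documents do not define the start of the clock. The decision falls on day 21, one infusion interval of 3 weeks (section 7.3.7, footnote 2). A Grade 3 event that has fallen to Grade 2 is shown against the Grade 2 row, although the documents do not say whether that row then governs.

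| Path of a Grade 3 non-hematological event | Hold sentence | Resume and stop sentences | Grade 2 row |
|---|---|---|---|
| Grade 2 on day 5, still Grade 2 | hold | resume | hold |
| Grade 2 on day 5, Grade 1 on day 18 | hold ends | resume | not applicable |
| Grade 2 on day 10, Grade 1 on day 13 | hold ends | resume | not applicable |
| Grade 2 on day 10, Grade 1 on day 18 | hold ends | stop | not applicable |
| Grade 2 on day 10, still Grade 2 | hold | stop | hold |

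The first path is the direct conflict: held by one sentence, re-dosed by the next. The fourth and fifth are the secondary ambiguity: the hold sentence read alone leaves restart open, while the later text stops the drug. The second and third give no conflict.

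For Grade 3 neutropenia the hold, resume and stop columns are the same. The last column drops out because the Grade 1 and 2 row is not applicable.

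**Can one patient meet all three instructions?** No. The resume and stop sentences are complementary: a patient satisfies one or the other, never both. The hold sentence and the Grade 2 row never disagree, because the Grade 2 row applies only while the event is above Grade 1. At most two different instructions remain. Running every path with Grade 2 and Grade 1 first reached on any day from 1 to 42 or never, and decisions on day 21 or day 42, gave only four outcome sets: resume; hold or resume; resume or stop; hold or stop.

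**The case against.** The best defence is that the text is one rule in sequence: hold, resume if either time limit is met, otherwise stop. On that reading the later sentences supply the time limit that the hold sentence lacks. For slow recovery this has real force. The pembrolizumab hold sentence contains only a hold, and the only restart instruction is the one that carries the 7-day and 14-day limits. An event reaching Grade 1 on day 18 can then be read, without contradiction, as discontinued. That part of the point is an ambiguity of drafting and is the weaker part.

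The defence does not remove the first path. If the resume sentence prevails, the hold to Grade 1 is not observed for an event that improves early to Grade 2, and a non-hematological event that began at Grade 3 is re-dosed at a grade at which the row above holds. If the hold sentence prevails, the 7-day alternative has no effect. Nothing in section 6.1.8 chooses between the two. The introductory text makes resumption subject to approval, but it gives no recovery grade on which to approve.

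Three limits on scope stand. Grade 4 non-hematological events have a judgment clause. Immune-related events and infusion reactions follow other tables. Neutropenia related to CLL marrow involvement is excluded from its row.

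**Conclusion.** The inconsistency is real and can be seen on the page. Grade 3 non-immune non-hematological toxicity and Grade 3 neutropenia each carry two recovery grades for restarting pembrolizumab. An event at Grade 2 by day 7 that stays there is told both to hold and to resume. The conflict with the Grade 2 row is confined to non-hematological events, and there it supposes that a downgraded event falls under that row. The time-limit ambiguity is secondary. The exact paths rest on counting days from onset; the clash between Grade 1 and Grade 2 does not.

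A reader might infer more than the documents support:

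- **That one patient may have to be re-dosed, held or permanently stopped.** The two time limits are joined by an or, so a patient at Grade 2 by day 7 never reaches the stop sentence. The three outcomes arise only across different patients.
- **That about 6 of 25 patients are affected.** Section 2.3.1 quotes 24% neutropenia, and 0.24 × 25 = 6. That rate combines Grades 3 and 4, is for single-agent ibrutinib, and says nothing about how many recover along a conflicting path.
- **That 13 of 18 infusions would be lost.** Infusions in weeks 0 to 51 number 51/3 + 1 = 18, and those from week 15 number (51 − 15)/3 + 1 = 13. This takes an arbitrary stop after week 12 and rests on the weaker, slow-recovery case.
- **That the safety results become uninterpretable, or patients drop out of the CR count.** Neither is shown. The boundary in section 10.2.3 counts dose-limiting toxicities, not discontinuations. A patient who stops after week 12 can already satisfy the evaluability wording in both section 6.1.9 and section 10.1.

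The number of patients affected cannot be derived from the documents. The point should be corrected because it concerns a safety-relevant instruction that cannot be followed as written.

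**What to change.** The sponsor should reconcile three entries in the section 6.1.8 table: the non-hematological Grade 2 row, the non-hematological Grade 3 or 4 row and the neutropenia Grade 3 row. Each should give one consistent condition for restarting pembrolizumab and one consistent condition for stopping it. The table should state whether an event that has fallen from Grade 3 to Grade 2 is governed by the Grade 2 row. It should also state the day from which the 7 and 14 days are counted. The choice of thresholds is the sponsor's; none is proposed here.

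The cost is an edit to one table, with the IRB review and staff training that any amendment requires (sections 13.2 and 12). No change to sample size or analysis follows from it.

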6.1.9 DURATION OF THERAPY

The duration of ibrutinib therapy will be up to 51 weeks.

The duration of therapy of pembrolizumab will be up to 51 weeks. Pembrolizumab dosing could be extended for up to 2 years if clinical benefit per investigator.

Patients will be considered evaluable if they complete at least 9 weeks or three infusions of pembrolizumab.

6.1.10 TRACKING OF DOSE

For ibrutinib there will be a Patient Compliance Pill Diary for oral medications provided to the subject when

each new supply of ibrutinib is dispensed.

For pembrolizumab there will be documentation in the patient's electronic medical record of dosing and a pharmacy dispensing/accountability log to determine the adherence.

6.2 STUDY AGENT ACCOUNTABILITY PROCEDURES

The study drugs will be stored in the Moffitt Investigational Pharmacy Department. There will be an accountability log for each drug. Any unused study drug will be destroyed on site per Investigational Pharmacy standard procedures.

7 STUDY PROCEDURES AND SCHEDULE

7.1 STUDY PROCEDURES

7.1.1 Overview

The Schedule of Events - Section 7.3.7 summarizes the trial procedures to be performed at each visit. Individual trial procedures are described in detail below. It may be necessary to perform these procedures at unscheduled time points if deemed clinically necessary by the investigator.

Furthermore, additional evaluations/testing may be deemed necessary by the PI and/or Merck or Janssen for reasons related to subject safety. In some cases, such evaluation/testing may be potentially sensitive in nature (e.g., HIV, Hepatitis C, etc.), and thus local regulations may require that additional consent be obtained from the subject. In these cases, such evaluations/testing will be performed in accordance with those regulations.

7.1.2 Informed Consent

Prior to any study procedure, informed consent must be obtained and documented by the subject's dated signature or by the subject's legally acceptable representative's dated signature on a consent form. The dated signature of the person conducting the consent discussion must also appear on the consent form.

7.1.3 Inclusion/Exclusion Criteria

Prior to any trial treatment, all inclusion and exclusion criteria will be reviewed and signed by the PI or Sub-Investigator to ensure the subject qualifies for the trial.

7.1.4 Medical History

A medical history will be obtained by the investigator or qualified designee. Medical history will include all active conditions, and any condition diagnosed that is considered to be clinically significant by the Investigator. Details regarding the disease for which the subject has enrolled in this study will be recorded separately and not listed as medical history.

7.1.4 Concomitant Medications Review

The investigator or qualified designee will record medication, if any, taken by the subject starting at screening until end of trial treatment. All medications related to reportable SAEs and ECIs should be recorded as defined in the SAE section of the protocol.

7.1.5 Post-Study Anticancer Therapy Status

The investigator or qualified designee will review all new CLL anti-neoplastic therapy initiated after the last dose of trial treatment. If a subject initiates a new anti-cancer therapy within 30 days after the last dose of trial treatment, the Safety Follow-up visit must occur before the first dose of the new therapy. Once new anti-cancer therapy has been initiated the subject will move into survival follow-up.

7.1.6 Adverse Event Review

The investigator or qualified designee will assess each subject to evaluate for potential new or worsening AEs as specified in the Trial Flow Chart and more frequently if clinically indicated. Adverse events will be collected from the time of consent, and will continue every 3 weeks during treatment. For adverse event collection after treatment discontinuation, see Section 8.3.

7.1.7 Full Physical Exam

The investigator or qualified designee will perform a complete physical exam during the screening period. Clinically significant abnormal findings should be recorded as medical history. A full physical exam should be performed during screening.

7.1.8 Directed Physical Exam

For cycles that do not require a full physical exam per the Trial Flow Chart, the investigator or qualified designee will perform a directed physical exam as clinically indicated prior to trial treatment administration.

7.1.9 Vital Signs

The investigator or qualified designee will take vital signs at screening, prior to the administration of each dose of trial treatment and at treatment discontinuation as specified in the Schedule of Events (Section 7.3.7). Vital signs should include temperature, pulse, respiratory rate, weight and blood pressure. Height will be measured at screening only.

7.1.10 Eastern Cooperative Oncology Group (ECOG) Performance Status

The investigator or qualified designee will assess ECOG status (see Appendix B) as specified in the Schedule of Events.

7.1.11 Assessment of Disease

Assessment of response (ORR) is a primary end point and will be reported using the latest Response Criteria Guidelines per the International Working Group of CLL. (Appendix C)

7.1.12 Laboratory Procedures/Assessment

Details regarding specific laboratory procedures/assessments to be performed in this trial are provided in the Schedule of Events. Tests specific to screening include hepatitis B and C panel, HIV evaluation at screening, serum *B*-HCG as defined, PT/INR and aPTT, urinalysis, CLL specific testing (ZAP-70, B-2 microglobulin, IgVH mutation, FISH), T3, free T4, and TSH.

7.1.13 Correlative Studies Blood Sampling

Blood samples will be collected pre-dose on Day 1, Week 6, Week 21, and end of ibrutinib therapy for immune testing per Schedule of Events. They will be performed at investigator's discretion if early study termination. For sampling requirements, see Section 7.2.

7.1.14 Laboratory Safety Evaluations

Laboratory testing for safety will be performed at time points per Schedule of Events. These tests include CBC/differential and CMP (albumin, BUN, creatinine, alkaline phosphatase, ALT, AST, CO₂, calcium, chloride, glucose, potassium, sodium, total bilirubin, total protein, LDH). Additional safety evaluations for tumor lysis syndrome (LDH, uric acid, phosphorus, Creatinine and BUN) will occur as defined in the Schedule of Events.

7.1.15 Tumor Imaging

Tumor imaging will consist of CT scan of the neck, chest, abdomen and pelvis. CT scan will be done at screening (if not done within 3 months prior to consent). Response assessments will be done at week 12 (+/-3 days), week 24 (+/-3 days), and after 51 weeks of ibrutinib. If the subject discontinues treatment early or progression of disease is suspected, CT will be done at the discretion of the investigator. Imaging during follow-up will be performed per investigator discretion.

7.1.16 Bone Marrow Biopsy

A bone marrow biopsy will be performed at screening (if not performed within 30 days), after the end of pembrolizumab and ibrutinib therapy (28-35 days after week 51). If subject discontinues treatment early or progression of disease is suspected, a bone marrow biopsy will be done at the discretion of the investigator. During follow-up, bone marrow biopsies will be performed per investigator discretion.

7.2 RESEARCH BLOOD SPECIMEN PREPARATION, HANDLING, AND STORAGE

Blood samples for correlative studies will be collected at baseline (prior to first dose of study drug), at week 9, week 12, and end of ibrutinib treatment. Peripheral blood will be utilized with an estimated volume of 50 cc collected in five green top tubes.

1. Preparation of Samples

Whole blood samples in 5 green top tubes (10ml/tube) will be received in the laboratory of [name]. Plasma will be isolated by centrifugation of the green top tubes for 5min at 1500rpm and lymphocyte isolation will be performed using Ficol gradient isolation for the purpose of immune testing.

2. Sample Storage

For storage, plasma will be held in 1.5 ml aliquots and placed in a -20C freezer. Lymphocytes will be frozen using 90% FBS and 10% DMSO and placed in a -80C freezer for short term storage. Long term storage of lymphocytes will be conducted utilizing liquid nitrogen.

3. Long-Term Use of Samples

Any isolated plasma and lymphocytes will be stored for the duration of the trial utilizing the short term method above and will be tested per protocol parameters outlined in Section 4.1. With the subject's permission, any samples remaining at the end of the trial will be placed in long term storage for use in future research. If any subject does not agree, that subject's remaining samples will be destroyed at the final closure of the trial.

4. Procedure for Clinical Trial Staff

The following procedure is recommended to be used for collaboration with the Research Science Lab:

- a. Notify the Research lab at least 2 days prior to the collection, using the template below.
Email to [contact] and cc [contact]
Follow up with a phone message to [name].
- b. Prepare a plastic bag with 5 green top tubes (tubes obtained from [name] lab). Attach label to tubes with MCC #, subject MRN, and date of collection. Each bag will have a label attached with the MCC #, subject MRN, DOB, initials, date/time of collection. Label should have research lab contact information. ("Contact [name] or [contact] for pick-up").
- c. Deliver bag of tubes to the Blood Draw area the day prior to collection.

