- Review of tests and assessment for TLS by the investigator or qualified designee.

7.3.2.6 Week 9

- Directed physical examination, vital signs and brief review of systems.
- Medication reconciliation.
- Toxicity/ AE assessment
- ECOG performance status assessment.
- Hematology (hemoglobin, HCT, RBC, WBC with differential [neutrophils, bands, lymphocytes, monocytes, eosinophils and basophils])
- Chemistry (ALT, AST, alkaline phosphatase, total bilirubin, LDH, calcium, bicarbonate, sodium, potassium, chloride, creatinine, BUN, total protein and albumin)
- Study drug administration (pembrolizumab and ibrutinib).

- Provide pill diary
- Serum chemistry profile and TLS evaluation by laboratory tests.
- Review of tests and assessment for TLS by the investigator or qualified designee.

7.3.2.7 Week 10

- Serum chemistry profile and TLS evaluation by laboratory tests.
- Review of tests and assessment for TLS by the investigator or qualified designee.

7.3.2.8 Weeks 12, 15, 18, 21

- Directed physical examination, vital signs and brief review of systems.
- Medication reconciliation.
- Toxicity/ AE assessment
- ECOG performance status assessment.
- Hematology (hemoglobin, HCT, RBC, WBC with differential [neutrophils, bands, lymphocytes, monocytes, eosinophils and basophils])
- Chemistry (ALT, AST, alkaline phosphatase, total bilirubin, LDH, calcium, bicarbonate, sodium, potassium, chloride, creatinine, BUN, total protein and albumin)
- Study drug administration (ibrutinib and pembrolizumab).
- CT scan week 12.
- Blood for correlative studies week 21
- Provide pill diary.

7.3.2.9 Week 24

- Directed physical examination, vital signs and brief review of systems.
- Medication reconciliation.
- Toxicity/ AE assessment
- ECOG performance status assessment.
- Hematology (hemoglobin, HCT, RBC, WBC with differential [neutrophils, bands, lymphocytes, monocytes, eosinophils and basophils])
- Chemistry (ALT, AST, alkaline phosphatase, total bilirubin, LDH, calcium, bicarbonate, sodium, potassium, chloride, creatinine, BUN, total protein and albumin)
- Tumor imaging (CT scans).

- Study drug administration (ibrutinib and pembrolizumab).
- Provide pill diary

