¹⁰ Tumor imaging will consist of CT of the neck, chest, abdomen and pelvis that will be performed at screening, if not done within 3 months prior to study entry. Response assessment will be done at week 12, week 24, and end of 51 weeks of treatment. CT scans may be performed at different intervals at investigator discretion (i.e. suspicion of progressive disease). Imaging studies post treatment discontinuation will be performed per investigator discretion (including end of treatment imaging assessment).

¹¹ Bone marrow biopsy will be performed at screening (if not performed within 30 days) and after the end of pembrolizumab and ibrutinib therapy (28-35 days after week 51). If subject discontinues treatment early or progression of disease is suspected, a bone marrow biopsy will be per investigator discretion. During follow-up, bone marrow biopsies will be performed per investigator discretion.

¹² Correlative studies. Please refer to Section 4.1 for biomarkers to be studied. They will be performed at baseline (prior to first dose of study drug), at week 6, week 21, and end of ibrutinib treatment. See Section 7.2 for correlative sample collection procedure. They will be performed at investigator's discretion if early study termination

¹³ Safety follow-up will be 90 days after the end of pembrolizumab treatment (may be at the regularly scheduled monthly visit that is nearest to 90 days if continuing on ibrutinib treatment) and 30 days post discontinuation of ibrutinib treatment. If the subject discontinues early, safety follow up must occur before first dose of the next therapy.

¹⁴ Follow-up after a subject has discontinued trial treatment will be every 12 weeks for 12 months.

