10.2.2 ANALYSIS OF THE SECONDARY ENDPOINT(S)

1. Change in T cell exhaustion and/or inhibition following treatment
2. Change in serum immunoglobulin levels following treatment
3. Progression free survival (PFS) and association with immune biomarkers

To determine if T cell exhaustion or inhibition have change due to treatment with the combination therapy at baseline immune testing to immune testing following completion of pembrolizumab and ibrutinib treatments (week 52) using paired t-tests with the null hypothesis being that there is no change in immune measurements following treatment (i.e., $H_0: \mu_d = 0$). If the assumptions of normality do not hold upon assessment, we will instead use nonparametric t-tests (i.e., Wilcoxon Sign Rank Test). Similar tests will be used to determine if changes in serum immunoglobulin levels also resulted following treatment. Tests will be one-sided as based on biology expect the change in immune response to be in one direction following treatment. Tests will be considered statistically significant if the p-value is less than 0.05. Assuming the study go on to stage II and enroll 25 patients, we will be able to detect a modest effect size of 0.60. To determine the association of progression free survival (PFS) with immune biomarkers (T cell exhaustion and/or inhibition, serum immunoglobulin levels), Cox proportional hazards models will be fit with assumption of proportional hazards (PH) assumption check via Schoenfeld residuals. If the PH assumption does not hold, we will rely on use of non-parametric methods (Kaplan-Meier curve with log-rank tests) where the biomarkers will be dichotomized for analysis based on an optimal cut-point determination based on an outcome-oriented approach outlined by Contral and O'Quigley (Contal C, O'Quigley J. An application of changepoint methods in studying the effect of age on survival in breast cancer. Computational Statistics & Data Analysis. 1999;30:253-70.). A Cox regression of the log hazard ratio on the continuous biomarker (assuming a standard deviation of 1 and an anticipated event rate of 0.50) will have 80% power at a 0.05 significance level to detect a regression coefficient equal to 0.79 (i.e., hazard ratio of 2.20).

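### Section 7.2 puts the two middle correlative blood draws at weeks 9 and 12, against weeks 6 and 21 elsewhere; following it would lose the only on-treatment sample taken before ibrutinib.

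*Combined protocol and SAP*

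**What the plan says.** The combined protocol and SAP gives the correlative sampling times in several places.

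- Section 7.2, on specimen preparation and handling: baseline, then "at week 9, week 12, and end of ibrutinib treatment".
- Section 7.1.13: "Blood samples will be collected pre-dose on Day 1, Week 6, Week 21, and end of ibrutinib therapy for immune testing per Schedule of Events". The same section refers the reader to Section 7.2 for sampling requirements.
- Section 7.3.7, Schedule of Events: the correlative row is marked at week 0, week 6, week 21 and the end-of-treatment visit. Footnote 12 says "They will be performed at baseline (prior to first dose of study drug), at week 6, week 21, and end of ibrutinib treatment", and then "See Section 7.2 for correlative sample collection procedure".
- Section 7.3.2, visit lists: correlative blood is listed at baseline (7.3.2.1), week 6 (7.3.2.4) and end of treatment (7.3.2.11). The combined list for weeks 12 to 21 (7.3.2.8) has "Blood for correlative studies week 21" and no week 12 draw. The week 9 list (7.3.2.6) has none.

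On the analysis side, Section 10.2.4 states that samples are taken at four time-points but does not name them. Section 10.2.2 compares baseline immune testing with testing "following completion of pembrolizumab and ibrutinib treatments (week 52".

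**The concern.** The two calendars agree only on the first and last draws. Section 7.2 is also the working instruction for notifying the laboratory, labelling the tubes and delivering them, and two other passages point to it. Staff arranging a draw are therefore directed to the one place where the weeks differ.

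Week 6 matters because ibrutinib and Prevnar 13 both begin then. A sample taken before dosing at that visit reflects pembrolizumab alone; every later sample reflects the combination. If Section 7.2 were followed, no such sample would exist, the week 21 sample would also be missing, and neither could be collected afterwards.

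**Working it through.** The plan states no figure to reproduce here. The check sets the calendars side by side and places each draw against treatment and vaccination.

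**Inputs**
- Pembrolizumab every 3 weeks from week 0 (Section 7.3.7, footnote 2).
- Ibrutinib starts at week 6 (Section 7.3.2.4).
- Prevnar 13 is given at week 6, day 1 (Sections 7.3.2.4 and 7.7).
- Visit window of plus or minus 3 days (Section 7.3.7).

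**Formulas**
- Prior infusions = number of infusion weeks (0, 3, 6, ...) earlier than the draw, taking each draw as pre-dose.
- Weeks since ibrutinib start and vaccine = draw week minus 6.

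| Calendar | Draw | Prior pembrolizumab infusions | Weeks since ibrutinib start and vaccine |
|---|---|---|---|
| Both | Week 0 | 0 | before both |
| 7.1.13, 7.3.2, 7.3.7 | Week 6, pre-dose | 2 (weeks 0, 3) | 6 − 6 = 0 |
| 7.1.13, 7.3.2, 7.3.7 | Week 21 | 7 | 21 − 6 = 15 |
| 7.2 | Week 9 | 3 | 9 − 6 = 3 |
| 7.2 | Week 12 | 4 | 12 − 6 = 6 |
| Both | End of ibrutinib | – | – |

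**Results**
1. Each calendar has 4 draws. They share 2, and together they cover 6 distinct times. The count of four in Section 10.2.4 therefore cannot show which is meant.
2. The visit window cannot reconcile them. Weeks 6 and 9 are 3 weeks apart, and weeks 12 and 21 are 9 weeks apart, against a tolerance of 3 days.
3. On-treatment draws before ibrutinib: 1 under the Schedule (week 6), 0 under Section 7.2.
4. First post-vaccine draw: 3 weeks after vaccination under Section 7.2, 15 weeks under the Schedule.

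**Which analyses depend on the middle draws**
- The primary endpoint, complete response, uses none of these samples.
- The paired tests in Section 10.2.2 use baseline and the draw after treatment, which both calendars contain.
- Section 10.2.4 uses the middle draws: summaries and responder comparisons at each time-point, paired changes between time-points, and a mixed model over all four.

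**The week 52 label**
The documents imply different ends of ibrutinib for a full course:
- The Schedule's dosing columns stop at week 51. With the end-of-treatment visit 0 to 7 days after the last dose (Section 7.3.2.11), the draw would fall at weeks 51 to 52.
- Last dispensing at week 51 plus 3 weeks of dosing (Section 5.4.1; Section 7.3.7, footnote 2): 51 + 3 = week 54.
- Up to 51 weeks of ibrutinib from week 6 (Section 6.1.9): 6 + 51 = week 57.
- 54 weeks of ibrutinib from week 6 (Section 4.1): 6 + 54 = week 60.

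Week 52 fits the first reading and precedes the end of ibrutinib under the other three. Sections 4.1 and 6.1.9 also allow pembrolizumab to be extended for up to 2 years, in which case the end of ibrutinib is not the completion of both drugs.

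**The case against.** The best reply is that the intended calendar is fairly clear. Section 7.1.1 makes the Schedule of Events the summary of procedures by visit, Section 7.1.13 defers to it, and footnote 12 cites Section 7.2 only for the collection procedure. One sentence in a handling section is the outlier. This stands as evidence of intent and supports correcting Section 7.2 rather than the other passages. It does not remove the need, because Section 7.1.13 also cites Section 7.2 for sampling requirements.

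Several stronger readings are tempting, and the documents do not support them.

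- *Patients will be sampled on different calendars and so will not be comparable.* Nothing indicates this. There is one site and one receiving laboratory, and either calendar applied uniformly would keep patients comparable with each other.
- *The secondary immune tests are compromised.* The paired comparison uses the two draws that both calendars share.
- *Week 52 is a third sampling calendar with no sample behind it.* Section 10.2.2 describes the draw after treatment is complete and attaches a week to it. Whether the week is wrong depends on an end of ibrutinib that the documents leave unresolved.
- *A planned pembrolizumab-alone contrast is lost.* No section specifies one, and the hypotheses in Section 3 concern the combination. What is lost is the only sample that would permit it.
- *Week 6 is stated to be pre-vaccine.* This is inferred from the pre-dose wording in Section 7.1.13 and from blood preceding Prevnar 13 in the week 6 list. Baseline is also pre-vaccine, but off treatment.

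It can also be said that the Schedule's calendar serves vaccine response less well, since it drops the draws at 3 and 6 weeks. That is a fair point. Sections 4.1 and 10.1 treat vaccine response as a secondary interest, and the Schedule lists no separate draw for it. The sponsor should therefore confirm the calendar.

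**Conclusion.** The contradiction is real and should be corrected, but its reach is limited. Two of four draws conflict. If Section 7.2 were followed, the exploratory analyses in Section 10.2.4 would lose the single on-treatment sample before ibrutinib, as well as the week 21 sample. The primary endpoint and the secondary baseline-to-end-of-treatment paired tests would be unaffected. The two-of-four figure counts dates; it does not measure any bias or loss of power, and Section 10.2.4 gives no power calculation against which to measure one.

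This rests on three assumptions: ibrutinib and vaccine both start at week 6, the week 6 draw precedes both, and the agreement of Section 7.1.13, the visit lists, the Schedule row and footnote 12 reflects what the sponsor intended. The week 52 label is a separate, smaller inconsistency that needs reconciling.

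**What to change.** 1. In Section 7.2, change the draws to baseline, week 6, week 21 and end of ibrutinib, matching the other passages. State that the week 6 sample is drawn before ibrutinib and the vaccine; Section 7.3.2.4 lets the medications be given in any order, so the sequence should be explicit.
2. Have the sponsor confirm that this calendar is intended, knowing that its first post-vaccine sample falls 15 weeks after vaccination.
3. Name the four time-points in Section 10.2.4.
4. In Section 10.2.2, reconcile the week 52 label with the end-of-treatment draw. The passages on the end of ibrutinib (Sections 4.1, 5.4.1, 6.1.9 and 7.3.7) must be reconciled with one another, and the text should say which draw is used for patients whose pembrolizumab is extended. This review takes no position on which treatment duration is right.

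The cost is a few wording changes. Correcting Section 7.2 adds no blood draws and leaves treatment unchanged.
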